8. BIOSPECIMEN STUDIES AND PROCEDURES

Biomarkers in patient tumors that can predict response to anti-PD-1 therapy are being actively investigated. One mechanism by which cancer tissues limit the host immune response is via upregulation of PD-1 ligand (PD-L1) and its ligation to PD-1 on antigen-specific CD8+ T cells [6, 7]. Recent research has reported that tumor regression after therapeutic PD-1 blockade requires pre-existing CD8+ T cells that are negatively regulated by PD-1/PD-L1-mediated adaptive immune resistance. [8] We propose that Sylatron will increase the response of pembrolizumab by increasing the tumor infiltrating CD3 and CD8 cells, and the level of PD-L1 and PD-1 expression in immune cells and cancer cells. In this study, we will first test the effect of Sylatron on tumor infiltrating lymphocytes, the level of PD-1 and PD-L1 expression, and clonality of the T-cell repertoire by comparing the tumor biopsies from baseline and three weeks of Sylatron treatment. Then we will correlate the change of PD-1, PD-L1 levels, immune score, and clonality of the T-cell repertoire from Sylatron treatment with clinical response.

Immunohistochemical (IHC) staining: The level of PD-1 and PD-L1 expression in tumor biopsy will be measured by immunohistochemical (IHC) staining at Merck laboratories. Immunohistochemical (IHC) staining, Digital image acquisition and analysis: The density of intratumoral total (CD3+) and cytotoxic (CD8+) T lymphocytes will be measured in the tumor interior (TI) and in the invasive margin (IM) of the three biopsied tumor samples. Immune cell densities will be obtained by immunohistochemistry and quantified using a biomarker imaging system in tandem with Image J processing software at Lombardi Comprehensive Cancer Center. Immune cell density in the TI and IM was converted to a binary score (0 as Low, 1 as High), with a cutoff threshold determined by the median density of CD3+ and CD8+ cells. We previously carried out a study on the association of intratumoral CD3 and CD8 cell density with recurrence free survival in patients with surgically resected Hepatocellular Carcinoma.

Next Generation Sequencing for T-cell receptor clonality: TCR sequencing and clonality quantification was performed as previously described [29,30] from tumor samples preserved using RNAlater (Qiagen) and stored at -80°C . DNA was isolated by mincing followed by extraction utilizing a DNeasy kit (Qiagen). TCR β CDR3 regions were amplified and sequenced using the survey ImmunoSeq assay in a multiplexed PCR method using 45 forward primers specific to TCR V β gene segments and 13 reverse primers specific to TCR J β gene segments. The experiments of measuring T-cell receptor clonality will be carried out at Lombardi Comprehensive Cancer Center.

PCR template abundance estimation: In order to estimate the average read coverage per input template in our multiplex PCR and sequencing approach, we will employ a set of approximately 850 unique types of synthetic TCR analog, comprising each combination of V β and J β gene segments.[30] These molecules will be included in each PCR reaction at very low concentration so that most unique types of synthetic template are not observed in the sequencing output. Using the known concentration of the synthetic template pool, we will simulate the relationship between the number of observed unique synthetic molecules and the total number of synthetic molecules will be added to reaction (this is very nearly one-to-one at the low concentrations we employed). These molecules then allowed us to calculate for each PCR reaction the mean number of sequencing reads obtained per molecule of PCR template, and thus to estimate the

number of rearranged T cell receptors per diploid genome (i.e., level of TIL infiltration) in the input material. The PCR analysis will be carried out in Lombardi Comprehensive Cancer Center.

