2.1.3 Correlative/Exploratory Objectives

- Determine the effect of Sylatron on anti- programmed death ligand-1 (PD-L1) level, immune score as determined by the density of CD3 and CD8 in the tumor interior and invasive margin(s) of the tumor, and the clonality of the T-cell repertoire.
- Determine the effect of Sylatron on anti-cancer immunity by measuring proliferation of CD8+ T cells, Granzyme B+ cells and proliferation of tumor cells, and correlating these changes with clinical response as determined by RECIST 1.1.

Hypothesis:

Therapies that target the programmed death-1 (PD-1) receptor have shown unprecedented rates of durable clinical responses in a sub-group of patients with various cancer types [1-5]. Biomarkers in patient tumor that will predict response to anti-PD-1 therapy are being actively investigated. One mechanism by which cancer tissues limit the host immune response is via upregulation of PD-1 ligand (PD-L1) and its ligation to PD-1 on antigen-specific CD8+ T cells [6, 7]. Recent research has reported that tumor regression after therapeutic PD-1 blockade requires pre-existing CD8+ T cells that are negatively regulated by PD-1/PD-L1-mediated adaptive immune resistance [8]. We propose that Sylatron will increase the response of pembrolizumab by increasing the tumor infiltrating CD3 and CD8 cells, and the level of PD-L1 and PD-1 expression in immune cells and cancer cells. In this study, we will first test the effect of Sylatron on tumor infiltrating lymphocytes, the level of PD-1 and PD-L1 expression, and clonality of the T-cell repertoire by comparing the tumor biopsies from baseline and three weeks of Sylatron treatment. Then we will examine whether the change of tumor infiltrating lymphocytes, the level of PD-1 and PD-L1 expression from Sylatron treatment correlates with clinical response in patient treated with pembrolizumab and Sylatron combination therapy.

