12.2.3 Definition of Exploratory Endpoints

- The density of CD3 and CD8 in the tumor interior and invasive margin of the tumor, and the clonality of the T-cell repertoire.
- Proliferation of CD8+ T cells, Granzyme B+ cells and proliferation of tumor cells.

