12.4.3 Analysis Plans for Exploratory Objectives

Density of CD3+ T cells and CD8+ T cells, proliferation of CD8+ T cells, Granzyme B+ cells and proliferation of tumor cells will be listed and summarized using the descriptive statistics (minimum, maximum, mean median, standard deviation). The CD8 + Tcells, Granzyme B+

cells, and proliferation of tumor cells will be correlated with the response by comparing the means of different groups using either 2-sample t-tests or non-parametric Wilcoxon rank-sum test, or the Chi-square test based on the distribution and structure of the data.

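### The High/Low immune score discards much of the information in CD3/CD8 density at an unspecified median, and no paired test of Sylatron's effect on density is named

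*Combined protocol and SAP*

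**What the plan says.** The exploratory objective in section 2.1.3 is Sylatron's effect on, among other things, an immune score built from CD3 and CD8 density. The method is "comparing the tumor biopsies from baseline and three weeks of Sylatron treatment".

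Section 8 gives the only rule for turning density into a score: density in the tumour interior and the invasive margin is "converted to a binary score (0 as Low, 1 as High), with a cutoff threshold determined by the median density" of CD3+ and CD8+ cells. It does not say whether the median comes from baseline samples, from each biopsy time, from all samples together or from elsewhere, or whether one value serves both times. The rule is in the past tense, and the next sentence begins "We previously carried out a study on the association of intratumoral CD3 and CD8 cell density with recurrence free survival", referring to resected hepatocellular carcinoma. The same section states the second use of the score: "Then we will correlate the change of PD-1, PD-L1 levels, immune score, and clonality of the T-cell repertoire from Sylatron treatment with clinical response".

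Section 12.2.3 defines the endpoint without any split: "The density of CD3 and CD8 in the tumor interior and invasive margin of the tumor". Section 12.4.3 summarises CD3+ and CD8+ density by minimum, maximum, mean, median and standard deviation. For CD8+ T cells, Granzyme B+ cells and tumour-cell proliferation against response it offers a two-sample t-test, a Wilcoxon rank-sum test, "or the Chi-square test based on the distribution and structure of the data". It does not mention the immune score, and it names no paired comparison of the two biopsies.

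**The concern.** Raised immune infiltration is the mechanism by which the trial expects Sylatron to lift the response rate from 17% to 35% (sections 1.4.1 and 1.4.4), and patients undergo a second biopsy to look for it. The natural analysis is the within-patient change in density. The plan describes that density but names no test for its change. What it intends to relate to response is the change in an immune score for which section 8 gives only a 0/1 rule. A patient whose density doubles without crossing the cut-off counts as unchanged. A patient who drifts across it counts the same as one with a large rise. With at most about 44 pairs, and fewer in practice, the trial cannot easily afford that loss. The unstated source of the median adds a second problem: one possible choice removes any group-level change in the score by construction.

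**Working it through.** **Number of pairs.** The documents give no power or sample size for any biomarker. The ceiling comes from the primary design: stop if 3 or fewer of 16 respond, and do not reject if 11 or fewer of 44 respond. Recomputed exactly, it has type I error 0.0461 (stated 0.046) and type II error 1 − 0.8091 = 0.1909 (stated 0.191), so the stated design reproduces. Complete pairs will be fewer than 44, because sections 7 and 8.1 let patients omit both biopsies. A stage-1 stop, with probability 0.716 at a 17% response rate, leaves 16 patients. I use 20 to 44 pairs as an assumed range.

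**Other assumptions, none of them in the documents.** One log-density (one cell type, one region), normally distributed; shift δ of 0.4 to 0.8 SD; within-patient correlation ρ of 0.3 to 0.7; two-sided 5% level.

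**Continuous analysis.** For a paired t-test the non-centrality is λ = δ√n / √(2(1 − ρ)). With δ = 0.5 and ρ = 0.5 the denominator is 1, and power is approximately Φ(λ − t), where t is the 97.5% point on n − 1 degrees of freedom:

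- n = 44: Φ(3.32 − 2.02) = Φ(1.30) ≈ 0.90
- n = 30: Φ(2.74 − 2.05) = Φ(0.69) ≈ 0.75
- n = 20: Φ(2.24 − 2.09) = Φ(0.15) ≈ 0.56

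**Binary analysis.** With a cut at the baseline median, the proportion High moves from 50% to Φ(0.5) = 69%, so an effect can show. It is tested by an exact McNemar test. Simulation with 6,000 trials per setting, δ = 0.5, ρ = 0.5:

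| Pairs | Paired t, density | Split, baseline median | Split, pooled median | Split, separate median at each time |
|---|---|---|---|---|
| 44 | 90% | 50% | 49% | 0% |
| 30 | 76% | 31% | 33% | 0% |
| 20 | 57% | 14% | 17% | 0% |

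Over the whole assumed range, the paired t-test has 30% to 100% power and the baseline-median split 9% to 96%. The split is lower in every setting.

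**Why the last column is zero.** Let a patients move Low to High, b move High to Low, and h be High at both times. Separate medians make half the paired patients High each time, so h + b = n/2 = h + a, hence a = b. McNemar's test depends on a − b, which is 0 whatever Sylatron does. This needs no distributional assumption, apart from no ties.

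**Link with response.** A median split of a normal variable has asymptotic efficiency 2/π = 0.64, so 44 split values carry about as much as 44 × 0.64 = 28 continuous ones. With 15 of 44 responders (0.35 × 44 = 15.4) and an assumed difference of 0.8 SD, power is 70% for a t-test on the value and 53% for a chi-square test on the split. After a stage-1 stop with 3 responders among 16 and an 8/8 split, the most extreme table (3 of 8 against 0 of 8) gives chi-square = 16 × (3 × 8)² / (8 × 8 × 3 × 13) = 3.69, below 3.84, so p < 0.05 is out of reach. A rank-sum test of 3 against 13 can reach p = 2/560 = 0.004.

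**The case against.** The strongest reply is that the objective is exploratory, has no stated power, and does not rest on the binary score alone. Density is the defined endpoint in sections 2.2.3 and 12.2.3 and is summarised as a continuous variable in 12.4.3. This stands, and it limits the point: a rise could be seen in the summaries. It does not remove the point, because those summaries are not a test of within-patient change, and none is named.

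A reader might infer that the plan makes a Sylatron effect impossible to detect. The documents do not support that. They do not say that the cut-off is the trial's own median, still less a separate one at each time; the past tense and the following sentence leave open a value carried over from the hepatocellular carcinoma study. Even with separate medians, individual patients can change category, so the correlation with response is weakened to one with a change of rank, not abolished.

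A reader might also infer that the binary score would go to a chi-square test with an inflated error rate. Section 12.4.3 does not send it there. With 44 patients split 22/22, the exact size of the uncorrected test swings from 2.1% to 10.8% across 4 to 15 responders. Averaged over binomial responder counts (ignoring the stage-1 stop) it is 5.2% at a response rate of 17% and 4.6% at 35%, which is close to nominal. Fisher's test would be no remedy: its average size is about 2.3%, its power in the example above is 27% against 53%, and with 3 of 16 responders its smallest p-value is 2 × 56/560 = 0.20.

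**Conclusion.** The point holds as a matter of efficiency and definition. The source of the median is unstated, the change in a High/Low score is to be correlated with response, and no paired analysis of density is specified. Under a 0.5 SD rise and correlation 0.5, any common-median split costs about 40 percentage points of power at 20 to 44 pairs. The loss varies with shift, correlation and number of pairs, all of which are assumed. Section 8 does not say how the scores for two cell types and two regions are combined; a sum of several 0/1 scores could lose less, and that was not calculated. The zero under separate medians is arithmetic, but applies to one possible reading and only to the proportion High. The primary endpoint, the two-stage design and the 44-patient target are not affected. This is an improvement worth making because it costs nothing, not a flaw that threatens the trial's main conclusion.

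**What to change.** In sections 8 and 12.4.3:

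- Make the within-patient change in continuous (log) CD3 and CD8 density, baseline to week 3, the analysis of the Sylatron effect. Name one test in advance, either the paired t-test or the Wilcoxon signed-rank test.
- Relate that continuous change to response with the Wilcoxon rank-sum test, also named in advance and not chosen after the data are seen.
- Keep High/Low as description only, with one cut-off fixed from the baseline samples before the week-3 samples are read and applied unchanged at week 3.

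The cost is wording. The densities are already to be measured at both times, and no patient, biopsy or assay is added.

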8.1 Tumor Biopsies

Archival tissue will be requested for all subjects. All subjects will have a biopsy performed of a safely accessible tumor before starting treatment (within 42 days of starting treatment on this protocol) and 3 weeks later prior to initiation of pembrolizumab (prior to Cycle 2 Day 1). Subjects for whom newly obtained samples cannot be provided (e.g. inaccessible tumor for biopsy or subject safety concerns) may omit both biopsies provided documentation of reason is clear in the medical record. In these instances, submission of an archived specimen only will suffice.

Analysis of molecular characteristics of baseline and on-treatment tumor samples. All patients will have biopsies performed of safely accessible tumors before starting treatment (within 42 days of starting treatment on this protocol) and 3 weeks later. Preferred biopsy is core biopsy; five 20-gauge core needle biopsies (diameter about 2 mm) with a throw length of approximately 2 cm will provide adequate tissue for study. Available paraffin embedded tumor tissue from prior biopsies or excisions will also be collected as pre-treatment comparator samples. Preferred archival material includes tissue obtained in the same manner as specified in this trial and with no systemic anti-tumor treatment received by the patient between the biopsy and their enrollment on this protocol. However, other archival tissue may also be collected.

Each set of core biopsies will be divided into 5 portions and processed as below for later analysis:

- 1) FFPE for histology and IHC (20% of the specimen, or 1 core biopsy)
- 2) Quick-frozen in OCT for immunohistology and protein studies (40% of the specimen, or 2 core biopsy): embedded in optimum cutting temperature (OCT) solution, frozen in liquid nitrogen, and then stored at -80° C.
- 3) Placed in RNA-later for RNA and RT-PCR (40% of the specimen, or 2 core biopsy).

Of note, patients who are on chronic anticoagulation will be required to hold anticoagulation prior to the biopsies being performed. Patients on warfarin must hold treatment for 5 days, but will be on low-molecular weight heparin (LMWH), 1mg/kg subcutaneously twice a day. The LMWH will continue until the last biopsy is complete. Patients may then resume warfarin the day after the last biopsy. Additionally, patients on LMWH will hold (*i.e.*, not receive) the dose of LMWH the morning of the procedure, but will resume the LMWH the evening of the day of the biopsy.

8.2 Blood Collections

Plasma, serum, and peripheral blood for PMBCs will be collected at the five scheduled time points: prior to treatment (1) C1D1, (2) C2D1, (3) C5D1 (4) C7D1 and (5) End of Treatment. PMBCs will be isolated by Ficoll gradient centrifugation and cryopreserved in 10% DMSO at -80°C for subsequent evaluation.

8.3 Storage of Biospecimens

Remaining specimens will be stored for future research once protocol described biospecimen-based studies are complete. This option will be presented to subjects in the informed consent.

8.4 Confidentiality of Biospecimens

Samples that are collected will be identified by a subject's sequence ID assigned at the time of registration to the trial. Any material issued to collaborating researchers will be anonymized and only identified by the subject's sequence ID.

9. CRITERIA FOR DISEASE EVALUATION

The following sections describe the recommended method to track disease response for solid tumor trials as per the Response Evaluation Criteria In Solid Tumors (RECIST) 1.1 (see Eisenhauer EA et al. *New response evaluation criteria in solid tumours: revised RECIST guideline (version 1.1)*. Eur J Can, 2009.45:p.228-247).

9.1 Measurable Disease

Measurable disease is defined as the presence of at least one measurable lesion. Measurable lesions are defined as those that can be accurately measured in at least one dimension (longest diameter to be recorded) as ≥ 20 mm by chest x-ray, as ≥ 10 mm with CT scan, or ≥ 10 mm with calipers by clinical exam. All tumor measurements must be recorded in millimeters (or decimal fractions of centimeters).

9.1.1 Malignant Lymph Nodes

To be considered pathologically enlarged and measurable, a lymph node must be ≥ 15 mm in short axis when assessed by CT scan (CT scan slice thickness recommended to be no greater than 5 mm). At baseline and in follow-up, only the short axis will be measured and followed.

9.2 Non-measurable Lesions

All other lesions (or sites of disease), including small lesions (longest diameter < 10 mm or pathological lymph nodes with ≥ 10 to < 15 mm short axis), are considered non-measurable disease. Bone lesions, leptomeningeal disease, ascites, pleural/pericardial effusions, lymphangitis cutis/pulmonitis, inflammatory breast disease, and abdominal masses (not followed by CT or MRI), are considered as non-measurable.

NOTE: Cystic lesions that meet the criteria for radiographically defined simple cysts should not be considered as malignant lesions (neither measurable nor non-measurable) since they are, by definition, simple cysts. 'Cystic lesions' thought to represent cystic metastases can be considered as measurable lesions, if they meet the definition of measurability described above. However, if non-cystic lesions are present in the same subject, these are preferred for selection as target lesions.

9.3 Target Lesions

All measurable lesions up to a maximum of 2 lesions per organ and 5 lesions in total, representative of all involved organs, should be identified as target lesions and recorded and measured at baseline. Target lesions should be selected on the basis of their size (lesions with the longest diameter), be representative of all involved organs, but in addition should be those that

lend themselves to reproducible repeated measurements. It may be the case that, on occasion, the largest lesion does not lend itself to reproducible measurement in which circumstance the next largest lesion which can be measured reproducibly should be selected. A sum of the diameters (longest for non-nodal lesions, short axis for nodal lesions) for all target lesions will be calculated and reported as the baseline sum diameters. If lymph nodes are to be included in the sum, then only the short axis is added into the sum. The baseline sum diameters will be used as reference to further characterize any objective tumor regression in the measurable dimension of the disease.

9.4 Non-target Lesions

All other lesions (or sites of disease) including any measurable lesions over and above the 5 target lesions should be identified as non-target lesions and should also be recorded at baseline. Measurements of these lesions are not required, but the presence, absence, or in rare cases unequivocal progression of each should be noted throughout follow-up.

9.5 Evaluation of Target Lesions

NOTE: In addition to the information below, also see section 4.3.2 in the international criteria proposed by the Response Evaluation Criteria in Solid Tumors (RECIST) Committee, version 1.1 (Eur J Cancer 45;2009:228-247) for special notes on the assessment of target lesions.

Complete Response (CR)	Disappearance of all target lesions. Any pathological lymph nodes (whether target or non-target) must have reduction in short axis to <10 mm.
Partial Response (PR)	At least a 30% decrease in the sum of the diameters of target lesions, taking as reference the baseline sum diameters
Stable Disease (SD)	Neither sufficient shrinkage to qualify for PR nor sufficient increase to qualify for PD, taking as reference the smallest sum diameters while on study
Progressive Disease (PD)	At least a 20% increase in the sum of the diameters of target lesions, taking as reference the smallest sum on study (this includes the baseline sum if that is the smallest on study). In addition to the relative increase of 20%, the sum must also demonstrate an absolute increase of at least 5 mm. (Note: the appearance of one or more new lesions is also considered progressions).

9.6 Evaluation of Non-Target Lesions

Complete Response (CR)	Disappearance of all non-target lesions and normalization of tumor marker level. All lymph nodes must be non-pathological in size (<10 mm short axis) NOTE: If tumor markers are initially above the upper normal limit, they must normalize for a subject to be considered in complete clinical response.
Non-CR/ Non-PD	Persistence of one or more non-target lesion(s) and/or maintenance of tumor marker level above the normal limits
Progressive Disease (PD)	Appearance of one or more new lesions and/or unequivocal progression of existing non-target lesions.

	Unequivocal progression should not normally trump target lesion status. It must be representative of overall disease status change, not a single lesion increase.
--	-------------------------------------------------------------------------------------------------------------------------------------------------------------------

Although a clear progression of “non-target” lesions only is exceptional, the opinion of the site investigator should prevail in such circumstances, and the progression status should be confirmed at a later time by the sponsor investigator.

